10.1 Regulatory and ethical compliance

This clinical study was designed and shall be implemented and reported in accordance with the International Conference on Harmonization (ICH) Harmonized Tripartite Guidelines for Good Clinical Practice (GCP), with applicable local regulations (including European Directive 2001/20/EC, US Code of Federal Regulations Title 21, and Japanese Ministry of Health, Labor, and Welfare), and with the ethical principles laid down in the Declaration of Helsinki.

10.2 Informed consent procedures

Eligible patients may be included in the study only after providing written (witnessed, where required by law or regulation), IRB/IEC-approved informed consent, or, if incapable of doing so, after such consent has been provided by a legally acceptable representative of the patient. In cases where the patient's representative gives consent, the patient should be informed about the study to the extent possible given his/her understanding. If the patient is capable of doing so, he/she should indicate assent by personally signing and dating the written informed consent document or a separate assent form. Informed consent must be obtained before conducting any study-specific procedures (i.e. all of the procedures described in the protocol). The process of obtaining informed consent should be documented in the patient's source documents.

Novartis will provide investigators a proposed informed consent form in a separate document that complies with the ICH GCP guideline and regulatory requirements and is considered appropriate for this study. Any changes to the proposed consent form suggested by the investigator must be agreed to by Novartis before submission to the IRB/IEC, and a copy of the approved version must be provided to the Novartis monitor after IRB/IEC approval.

10.3 Responsibilities of the investigator and IRB/IEC

The protocol and the proposed informed consent form must be reviewed and approved by a properly constituted Institutional Review Board/Independent Ethics Committee/Research Ethics Board (IRB/IEC) before study start. A signed and dated statement that the protocol and informed consent have been approved by the IRB/IEC must be given to Novartis before study initiation. Prior to study start, the investigator is required to sign a protocol signature page confirming his/her agreement to conduct the study in accordance with these documents and all of the instructions and procedures found in this protocol and to give access to all relevant data and records to Novartis monitors, auditors, Novartis Clinical Quality Assurance representatives, designated agents of Novartis, IRBs/IECs, and regulatory authorities as required. If an inspection of the clinical site is requested by a regulatory authority, the investigator must inform Novartis immediately that this request has been made.

10.4 Publication of study protocol and results

Novartis assures that the key design elements of this protocol will be posted in a publicly accessible database such as clinicaltrials.gov. In addition, upon study completion and finalization of the study report, the results of this trial will be either submitted for publication and/or posted in a publicly accessible database of clinical trial results.

It is Novartis' policy for multi-center clinical trials that the first publication is based on consolidated data from all centers, analyzed as stipulated in the protocol and agreed upon by investigators before trial initiation.

11 Protocol adherence

Investigators ascertain they will apply due diligence to avoid protocol deviations. Under no circumstances should the investigator contact Novartis or its agents, if any, monitoring the trial to request approval of a protocol deviation, as requests to approve deviations will not be granted.

This protocol defines the study objectives, the study procedures and the data to be collected on study participants. Under no circumstances should an investigator collect additional data or conduct any additional procedures for any research related purpose involving any investigational drugs.

If the investigator feels a protocol deviation would improve the conduct of the study, this must be considered a protocol amendment, and unless such an amendment is agreed upon by Novartis and approved by the IRB/IEC, it cannot be implemented. All significant protocol deviations will be recorded and reported in the CSR.


13 Appendix 1: Clinically notable laboratory values and vital signs

The following criteria will be used to define expanded limits and notable abnormalities of key laboratory tests. No specific action is pre-defined within this protocol to respond to specific abnormal laboratory values, as it will be decided by the investigator/qualified site staff whether and which specific action needs to be taken to respond to any abnormal values, taking into account the overall status of the subject.

Liver Function and Related Variables

ALT (SGPT):	> 3 x Upper Limit of Normal (ULN)
AST (SGOT):	> 3 x ULN
Total bilirubin:	> 2 x ULN
Alkaline phosphatase:	> 2.5 x ULN

Renal Function and Electrolyte Variables

Creatinine (serum):	> 1.5 x ULN
Potassium:	> 6 mmol/L or < 3 mmol/L
Sodium:	> 160 mmol/L or < 115 mmol/L

Hematology Variables

Hemoglobin:	≥ 20 g/dL decrease from baseline
Platelet count:	< Lower Limit of Normal (LLN)
White blood cell count:	< 0.8 x LLN
Neutrophils:	< 0.9 x LLN
Eosinophils:	> 1.1 x ULN
Lymphocytes:	> 1.1 x ULN

Urinalysis Variable

Protein urine dipstick:	+++ (* ++ is ≥ 100 mg/dL)
-------------------------	--------------------------------

Blood Pressure and Heart Rate

Normal blood pressure will be defined as a systolic pressure of 90 to <120 mmHg, and a diastolic blood pressure of 60 to <80 mmHg. Notable blood pressure will be hypertension (systolic blood pressure of ≥ 140 mmHg and/or diastolic blood pressure of ≥ 90 mmHg) or hypotension (systolic blood pressure of <90 mmHg and/or a diastolic blood pressure of <60 mmHg). A blood pressure indicative of prehypertension (systolic blood pressure of 120 to

<140 mmHg and/or diastolic blood pressure of 80 to <90 mmHg) will not be regarded as notable.

A normal pulse rate will be defined as a rate of 60 to 100 beats per minute (bpm). Notable pulse rates are a rate below 60 bpm (bradycardia) or above 100 bpm (tachycardia). Whether action needs to be taken to address notable vital signs will be decided by the investigator, taking into account the overall status of the patient. No specific action is foreseen as part of the study protocol.

14 Appendix 2: Liver event definitions and follow-up requirements

Table 14-1: Liver Event Definitions

	Definition/ threshold
Adverse event of special interest	
Laboratory values	ALT or AST > 3 x ULN ALP > 2 x ULN TBL > 1.5 x ULN
Medically significant event (SAE)	
Laboratory values	ALT or AST > 5 x ULN (with or without TBL > 2 x ULN [mainly conjugated fraction]) ALP > 5 x ULN (with or without TBL > 2 x ULN [mainly conjugated fraction]) TBL > 3 x ULN Potential Hy's Law cases (defined as ALT/AST > 3 x ULN and TBL > 2 x ULN [mainly conjugated fraction] without notable increase in ALP to > 2 x ULN)
Adverse events	Any clinical event of jaundice (or equivalent term) ALT or AST > 3 x ULN accompanied by general malaise, fatigue, abdominal pain, nausea, or vomiting, or rash with eosinophilia Any event that links to a preferred term (PT) in the MedDRA dictionary falling under the SMQ sub-module "Drug-related hepatic disorders – severe events only"* or any "Hy's law case" PT

* These events cover the following: hepatic failure, fibrosis and cirrhosis, and other liver damage-related conditions; non-infectious hepatitis; benign, malignant and unspecified liver neoplasms

Table 14-2: Liver Event Follow Up Requirements

Criteria	Event type	Actions required	Follow-up monitoring
Potential Hy's Law case ^a	Medically significant	Discontinue the study drug immediately Hospitalize, if clinically appropriate Report to Novartis as an SAE Establish causality	ALT, AST, TBL, Alb, PT, ALP and γ GT until resolution ^c (frequency at investigator discretion)
ALT or AST			
> 8 x ULN	Medically significant	Repeat LFT within 48 hours If elevation persists, discontinue the study drug immediately Hospitalize if clinically appropriate Report to Novartis as an SAE Establish causality	ALT, AST, TBL, Alb, PT, ALP and γ GT until resolution ^c (frequency at investigator discretion)
> 5 to \leq 8 x ULN	Medically significant	Repeat LFT within 48 hours If elevation persists for more than 2 weeks , discontinue the study drug Report to Novartis as an SAE Establish causality	ALT, AST, TBL, Alb, PT, ALP and γ GT until resolution ^c (frequency at investigator discretion)
> 3 x ULN accompanied by symptoms ^b	Medically significant	Discontinue the study drug immediately Hospitalize if clinically appropriate Report to Novartis as an SAE Establish causality	ALT, AST, TBL, Alb, PT, ALP and γ GT until resolution ^c (frequency at investigator discretion)
> 3 to \leq 5 x ULN (patient is asymptomatic)	AESI	Central laboratory to report to Investigator & Novartis Repeat LFT once or twice in the week If elevation persists, establish causality	Investigator discretion Monitor LFT within 1 to 4 weeks or at next visit
\leq 3 x ULN (patient is asymptomatic)	N/A	Repeat LFT at next visit	
ALP (isolated)			
> 5 x ULN	Medically significant	Repeat LFT within 48 hours If elevation persists, report to Novartis as an SAE Establish causality	Investigator discretion Monitor LFT within 1 to 4 weeks or at next visit
> 2 to \leq 5 x ULN (patient is asymptomatic)	AESI	Central laboratory to report to Investigator & Novartis Repeat LFT once or twice in the week If elevation persists, establish causality	Investigator discretion Monitor LFT within 1 to 4 weeks or at next visit
\leq 2 x ULN (patient is asymptomatic)	N/A	Repeat LFT at next visit	

Criteria	Event type	Actions required	Follow-up monitoring
asymptomatic)			
TBL (isolated)			
> 3 x ULN	Medically significant	Repeat LFT within 48 hours If elevation persists, discontinue the study drug immediately Hospitalize if clinically appropriate Report to Novartis as an SAE Establish causality	ALT, AST, TBL, Alb, PT, ALP and γ GT until resolution ^c (frequency at investigator discretion) Test for hemolysis (e.g., reticulocytes, haptoglobin, unconjugated [indirect] bilirubin)
> 1.5 to \leq 3 x ULN (patient is asymptomatic)	AESI	Central laboratory to report to Novartis Repeat LFT once or twice in the week. If elevation persists, establish causality	investigator discretion Monitor LFT within 1 to 4 weeks or at next visit
\leq 1.5 x ULN (patient is asymptomatic)	N/A	Repeat LFT at next visit	
Preferred terms			
Jaundice	Medically significant	Discontinue the study drug immediately Hospitalize the patient Report to Novartis as an SAE Establish causality	ALT, AST, TBL, Alb, PT, ALP and γ GT until resolution ^c (frequency at investigator discretion)
"Drug-related hepatic disorders - severe events only" SMQ AE	Medically significant	Discontinue the study drug hospitalization if clinically appropriate Report to Novartis as an SAE Establish causality	Investigator discretion

^a Elevated ALT/AST > 3 x ULN and TBL > 2 x ULN but with no notable increase in ALP to > 2 x ULN

^b General malaise, fatigue, abdominal pain, nausea, or vomiting, rash with eosinophilia

^c Resolution is defined as an outcome of one of the following: return to baseline values, stable values at three subsequent monitoring visits at least 2 weeks apart, remain at elevated level after a maximum of 6 months, liver transplantation, and death.

15 Appendix 3: The PASI Scoring System

Body Region	Erythema (E)	Thickening (plaque elevation, induration, I)	Scaling (desquamation, D)	Area score (based on true area %, A)*
Head (H)†	0=none	0=none	0=none	0 = 0%
	1=slight	1=slight	1=slight	1 = 1-9%
	2=moderate	2=moderate	2=moderate	2 = 10-29%
	3=severe	3=severe	3=severe	3 = 30-49%
	4=very severe	4=very severe	4=very severe	4 = 50-69%
				5 = 70-89%
			6 = 90-100%	
Trunk (T)‡	0=none	0=none	0=none	0 = 0%
	1=slight	1=slight	1=slight	1 = 1-9%
	2=moderate	2=moderate	2=moderate	2 = 10-29%
	3=severe	3=severe	3=severe	3 = 30-49%
	4=very severe	4=very severe	4=very severe	4 = 50-69%
				5 = 70-89%
			6 = 90-100%	
Upper limbs (U)	0=none	0=none	0=none	0 = 0%
	1=slight	1=slight	1=slight	1 = 1-9%
	2=moderate	2=moderate	2=moderate	2 = 10-29%
	3=severe	3=severe	3=severe	3 = 30-49%
	4=very severe	4=very severe	4=very severe	4 = 50-69%
				5 = 70-89%
			6 = 90-100%	
Lower limbs (L)§	0=none	0=none	0=none	0 = 0%
	1=slight	1=slight	1=slight	1 = 1-9%
	2=moderate	2=moderate	2=moderate	2 = 10-29%
	3=severe	3=severe	3=severe	3 = 30-49%
	4=very severe	4=very severe	4=very severe	4 = 50-69%
				5 = 70-89%
			6 = 90-100%	

* Percentage (not score) of body region (not whole body) affected will be entered in the eCRF

† Neck is assessed as part of the Head (H) body region.

‡ Axillae and groin are assessed as part of the Trunk (T) body region.

§ Buttocks are assessed as part of the Lower limbs (L) body region.

16 Appendix 4: The IGA mod 2011 rating scale

Score	Short description	Detailed description
0	Clear	No signs of psoriasis. Post-inflammatory hyperpigmentation may be present.
1	Almost clear	Normal to pink coloration of lesions; no thickening; no to minimal focal scaling.
2	Mild	Pink to light red coloration; just detectable to mild thickening; predominantly fine scaling.
3	Moderate	Dull bright red, clearly distinguishable erythema; clearly distinguishable to moderate thickening; moderate scaling.
4	Very Severe	Bright to deep dark red coloration; severe thickening with hard edges; severe / coarse scaling covering almost all or all lesions.

Note: Involvement of nails is not part of the assessment.

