7.2 Serious adverse event reporting

To ensure patient safety, every SAE, regardless of causality, occurring after the patient has provided informed consent and until 30 days after the last study visit must be reported to

Novartis within 24 hours of learning of its occurrence. Any SAEs experienced after the 30-day period should only be reported to Novartis if the investigator suspects a causal relationship to study treatment.

Recurrent episodes, complications, or progression of the initial SAE must be reported as follow-up to the original episode, regardless of when the event occurs. This report must be submitted within 24 hours of the investigator receiving the follow-up information. An SAE that is considered completely unrelated to a previously reported one should be reported separately as a new event.

The investigator will complete the SAE Report Form in English, assess the relationship to the study treatment and send the completed and signed form by fax within 24 hours to the local Novartis Drug Safety and Epidemiology Department Novartis (DS&E). The original and the duplicate copies of the SAE Form, and the fax confirmation sheet will be kept with the case report forms at the study site.

Follow-up information will be sent to the same person to whom the original SAE Form was sent, re-stating the date of the original report. A new SAE Form will be used (stating that this is a “follow-up”). The follow-up report should describe whether the event is resolved or continues, if and how it was treated, and whether the patient continued or discontinued study participation. The form and fax confirmation sheet will be retained at the study site.

If the SAE is not previously documented in the Investigator’s Brochure or Package Insert (new occurrence) and is thought to be related to the investigational treatment, a Drug Safety and Epidemiology Department associate may urgently require further information from the investigator for Health Authority reporting. Novartis may need to issue an Investigator Notification to inform all investigators involved in any study with the same investigational treatment that this SAE has been reported. Suspected Unexpected Serious Adverse Reactions (SUSARs) will be collected and reported to the competent authorities and relevant ethics committees in accordance with Directive 2001/20/EC or as per national regulatory requirements in participating countries.

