7.3 Liver safety monitoring

To ensure patient safety and enhance reliability in determining the hepatotoxic potential of an investigational drug, a standardized process for identification, monitoring and evaluation of liver events has to be followed.

Liver events are divided into two categories:

- Liver events of special interest, which consist of liver function test (LFT) elevations.
- Medically significant liver events that are considered as serious adverse events and consist of marked elevations of LFTs and / or pre-specified adverse events.

Please refer to [Table 14-1](#) in [Appendix 2](#) for complete definitions of liver events.

Any liver event that meets the criteria for “**medically significant**” event, as outlined in [Table 14-1](#) of [Appendix 2](#), should follow the **standard procedures for SAE reporting** as described in [Section 7.2](#).

Every liver event as defined in [Table 14-1](#) of [Appendix 2](#) should be followed up by the investigator or designated personal at the trial site as summarized below.

- Repeat the LFT to confirm elevation as appropriate.
- Discontinue the investigational drug if appropriate.
- Hospitalize the patient if appropriate.
- Assess the causality of the liver event via exclusion of alternative causes (e.g., disease, co-mediations).
- An investigation of the liver event needs to be followed until resolution.

These investigations can include serology tests, imaging and pathology assessments, hepatology consultancy, based on the investigator's discretion. All follow-up information and the procedures performed should be recorded on appropriate CRF pages, including the liver event overview CRF pages.

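### Table 14-2 makes the SAE report for isolated ALP above 5 x ULN wait for a repeat test, although Section 7.3 and Table 14-1 class every such result as an SAE due within 24 hours

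*Protocol*

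**What the plan says.** Four places in the current protocol bear on one laboratory result, an isolated ALP above 5 x ULN.

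- **Appendix 2, Table 14-1 (definitions).** Under the block headed "Medically significant event (SAE)" the table lists "ALP > 5 x ULN (with or without TBL > 2 x ULN [mainly conjugated fraction])". It sets no condition on confirmation or persistence.
- **Section 7.3 (liver safety monitoring).** The second category of liver event is described as "Medically significant liver events that are considered as serious adverse events". Any event meeting the Table 14-1 criteria for that category is to follow the "standard procedures for SAE reporting" in Section 7.2.
- **Section 7.2 (SAE reporting).** Every SAE, whatever its cause, must reach "Novartis within 24 hours of learning of its occurrence".
- **Appendix 2, Table 14-2 (follow-up), isolated ALP above 5 x ULN.** The event type is again medically significant. The actions are a repeat liver test within 48 hours and then: "If elevation persists, report to Novartis as an SAE".

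**The concern.** The definition table and Section 7.3 make the first ALP result above 5 x ULN an SAE, and the 24-hour clock starts when the site learns of it. The follow-up table makes the report depend on a second result that may not exist for another 48 hours. A site cannot obey both when the rise is transient, and may miss the deadline when it persists.

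What is at stake is the completeness, timing and consistency of SAE reporting. SAP 2.8.1 compares patients with SAEs between the Cw6 cohorts by logistic regression and total SAEs by Poisson regression, in support of a stated secondary objective on safety. If some sites follow Section 7.3 and others the table row, the same event counts as an SAE at one site and not at another.

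**Working it through.** There is no statistical figure to reproduce. The check compares the texts and adds up the stated time limits.

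**1. Does the Table 14-1 entry cover an isolated rise?** Yes. It applies with or without raised bilirubin, so the word isolated in Table 14-2 does not take the event out of the SAE category. Table 14-2 itself keeps the medically significant label.

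**2. Is the condition general in Table 14-2?** No. The table has eight medically significant rows:

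| Row | Repeat within 48 h | What persistence governs | SAE report |
|---|---|---|---|
| Potential Hy's Law case | no | nothing | unconditional |
| ALT/AST > 8 x ULN | yes | stopping the drug | unconditional |
| ALT/AST > 5 to ≤ 8 x ULN | yes | stopping the drug (after 2 weeks) | unconditional |
| ALT/AST > 3 x ULN with symptoms | no | nothing | unconditional |
| **ALP > 5 x ULN, isolated** | **yes** | **the SAE report** | **conditional** |
| TBL > 3 x ULN, isolated | yes | stopping the drug | unconditional |
| Jaundice | no | nothing | unconditional |
| Severe hepatic SMQ event | no | nothing | unconditional |

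That is 7 unconditional and 1 conditional. Of the 4 rows that ask for a repeat within 48 hours, 3 still have an unconditional report. In the ALT/AST > 8 x ULN row, for example, the actions run: "If elevation persists, discontinue the study drug immediately Hospitalize if clinically appropriate Report to Novartis as an SAE". The capitalised verbs mark separate actions. In the ALP row the verb is lower case and belongs to the if-clause. Line breaks inside the cells are lost in the available text, so this reading rests on the capitalisation and sentence structure.

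**3. Effect on counting.** A rise that has gone at the repeat counts as 1 SAE under Section 7.3 and Table 14-1, and 0 if the site follows the ALP row.

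**4. Effect on timing for a persistent rise.** The deadline under Section 7.2 is 24 h after the first result becomes known. Laboratory turnaround is ignored.

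- Repeat at 48 h, report sent at once: 48 − 24 = 24 h late.
- Repeat at 48 h, and the site (by assumption) restarts the 24-hour clock there: 48 + 24 − 24 = 48 h late.
- Repeat done and reported within 24 h: no delay.

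**5. How many patients?** The documents give no event rate. As an assumption only, over 406 enrolled patients:

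- 0.1%: 406 × 0.001 = 0.4
- 0.5%: 406 × 0.005 = 2.0
- 1%: 406 × 0.01 = 4.1

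The number of scheduled post-baseline ALP tests is at most 6 × 406 (visits 7 to 12) + 4 × 306 (E1 to E4) = 2,436 + 1,224 = 3,660, with no dropout. That counts opportunities to detect a rise, not events. Exclusion criterion 16 removes patients with ALP above 2 x ULN at screening, which points to few events.

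**The case against.** The strongest reply is that the condition is deliberate. The ALP row is the only medically significant row with no instruction to stop the drug; it has no hospitalization step, and its monitoring matches the rows for events of special interest. The whole row looks set lighter, with confirmation before escalation. Section 7.3 also lists "Repeat the LFT to confirm elevation as appropriate". On this view Table 14-1 may simply lack the word confirmed.

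The intent may indeed have been that, but no text says so. Section 7.3 names Table 14-1, not Table 14-2, as the trigger for SAE reporting, and nothing lets the follow-up table override Section 7.2. The Section 7.3 bullet is one of several follow-up steps listed after the reporting instruction; it does not qualify that instruction. The rule in Section 7.1 on when abnormal laboratory values are adverse events does not help either, since clinical significance is one of its criteria and Table 14-1 already classes this value as medically significant.

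A second reply is that the row does not forbid earlier reporting, so a site applying Sections 7.2 and 7.3 would report on time. That stands: the harm arises only where a site works from the follow-up table. That table is, however, what a site would naturally consult for actions after a liver result.

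**Conclusion.** The concern holds. Two current instructions give different answers for the same result, and the texts that control SAE reporting (Sections 7.2 and 7.3 with Table 14-1) make the report unconditional.

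The point is minor. It touches one row of eight and probably a handful of patients at most; that estimate rests on an assumed rate. The delay of 24 to 48 hours applies to a persistent rise with the repeat taken at the full 48 hours, and its upper end needs the further assumption that the site restarts its clock. The result itself is not lost: Section 7.3 puts follow-up on the liver event CRF pages, and a value above 5 x ULN exceeds the 2.5 x ULN notable limit in SAP Table 2.8.3, so it appears in the listings. The PASI 90 analysis is not affected.

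**What to change.** In Table 14-2, isolated ALP above 5 x ULN, delete the persistence condition so that the SAE instruction stands alone, worded as in the other seven medically significant rows. Keep the repeat within 48 hours as a follow-up step. Thresholds, drug-stopping rules and footnotes stay as they are.

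The cost is one line of wording, by amendment or by a clarification letter to sites, and at most a few more SAE forms. No procedure is added.

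If the sponsor did intend confirmation first for isolated ALP, the alternative is to write that condition into Table 14-1 and Section 7.3 and state when the 24-hour clock starts. That changes more text and would set ALP apart from the other liver criteria, so the one-row change is preferable.
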